11.3. ANALYSIS AND EVALUATION

11.3.1. Statistical Analysis

Evaluation elements are defined as the questions on the CRF/eCRF. The SAP lists all evaluation elements and secondary elements which will be based on calculations between two or more evaluation elements.

All quantitative variables, including those based on calculations (secondary elements), will be analyzed with a case summary evaluation before the detailed characteristics and parameters can be evaluated. A case summary contains a listing of the number of valid cases/values, missing cases/values (if any) and total cases/values in the specific analysis. In general, as central position parameter for quantitative variables the mean, median and mode will be analyzed. As variation parameter the standard deviation, 95% confidence interval of the mean, interquartile range and range (based on maximum and minimum) will be calculated. All quantitative variables will be assessed for normality using the Shapiro-Wilk test. For optional visualization of quantitative variables, box-and-whisker plots will be used. Additional analyses like skewness and kurtosis measures or standard errors are optional also.

All qualitative variables, including those based on summaries (secondary elements), will be analyzed listing the proportions, frequencies, column and row totals, and missing proportion, if any.

The SAP reflects this approach and specifies the variables characteristics (quantitative or qualitative) in detail together with the related analysis strategy. This also includes calculation and summaries based on primary elements and the required analysis.

11.3.2. Primary Analysis / Endpoint

The objective of the clinical investigation is to demonstrate non-inferiority (equal or better) of the ASES Shoulder Score in relationship to the officially cleared indications in comparison to respective clinical outcome data in the scientific literature.

[figure not shown]
Data collection of ASES Shoulder Score will start pre-operatively and will be collected according to schedule in Table 1. This will be repeated annually in all subjects who have the total or partial prosthesis with full or partial implant survival (including all subjects without removal of all endo-prosthesis components).

The 24 months post-operative results for subjects implanted with ReUnion TSA System will be compared to a historical group and results reported by respective clinical outcome data in the scientific literature. The benchmark sources and values will serve as the control group for the ReUnion TSA System subjects.

Higher ASES Shoulder Score results are linked to better subject results and vice versa.

The clinical investigation endpoint is non-inferiority to the control, meaning the clinical investigation result should be equal or better than the control. In this clinical investigation, an equal or better ASES Shoulder Score result means equal or more (\geq). As only results from samples will be captured, results are mostly estimates of the true population parameter. These estimates vary by a certain area, where it is expected that the true population parameter falls within. Based on this, it is required to specify a lower limit for the acceptable difference or zone of indifference, denoted as $-\theta$.

Hypotheses are developed to allow for a comparison of the 24 months post-operative ASES Shoulder Score effectiveness / performance between the two underlying populations. The 24 months post-operative ASES Shoulder Score is the primary endpoint of this clinical investigation. Hypothesis tests will be one-sided with a significance level α of 5%.

Hypothesis	Equations	Interpretation
Null (H_0)	$A - B < -\theta$	Central tendency of A is inferior to the central tendency of B.
	ReUnion TSA System – Control (Benchmark) $< -\theta$	
Alternative (H_1)	$A - B \geq -\theta$	Central tendency of A is non-inferior to the central tendency of B.
	ReUnion TSA System – Control (Benchmark) $\geq -\theta$	
		
Possible Evidence (p)	Possible Decisions	Possible Conclusions – ASES score
p-value $> \alpha$ (0.05)	Fail to reject null hypothesis (H_0)	ReUnion TSA System $<$ Control (Benchmark) Insufficient evidence to reject the null hypothesis ($H_0: A - B < -\theta$) at the pre-determined significance level of 5%.
p-value $\leq \alpha$ (0.05)	Reject null hypothesis (H_1)	ReUnion TSA System \geq Control (Benchmark) Sufficient evidence to reject the null hypothesis ($H_0: A - B < -\theta$) at the pre-determined significance level of 5%.

To test non-inferiority, the 24 months mean ASES Shoulder Score result of the ReUnion TSA System group will be compared to the mean estimate of the control group, 82.16 points.

To be able to identify an acceptable difference or zone of indifference ($-\theta$), the pooled standard deviation of the ASES Shoulder Score result at 24 months post-operative in the control group (Benchmark) was used as lower limit (pooled standard deviation of control is 16.76 points). The lower maximum acceptable difference ($-\theta$) is 51.87 points (mean of control - θ or 82.16 - 16.76 = 65.40 points).

Based on the underlying distribution of the data and the result of the normality assessment, either the parametric one-sample t-test or the non-parametric one-sample sign test will be used to compare the 24 months post-operative ASES Shoulder Score results of the ReUnion TSA System against the value of 65.40 points.

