Results will be presented using summary tables and optionally supported by graphs. For detailed information per variable, see SAP.

[figure not shown]
The primary endpoint of the clinical investigation is to demonstrate non-inferiority of the device to the selected literature controls, as measured by the ASES Shoulder Score at 24 Months post-operative. Specifically, the proposed study will test the null hypothesis that the population mean is 82.16 points. The criterion for significance (alpha) is set at 0.05. With the sample size of 10 cases, the clinical investigation will have power of 80.3% to yield a statistically significant result. This computation assumes that the population from which the sample will be drawn has a mean of 82.16 points with a standard deviation of 16.76 points. The observed value will be tested against a theoretical value (lower limit - θ) of 65.40 points. To account for an estimated appropriate overall drop-out rate, Stryker intends to enroll the calculated number of subjects, multiplied by the number of cleared indications (5) to reflect the underlying subject population adequately.

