p-value > α (0.05)	Fail to reject null hypothesis (H0)	ReUnion TSA System < Control (Benchmark) Insufficient evidence to reject the null hypothesis (H0: A - B < - θ) at the pre-determined significance level of 5%.
p-value \leq α (0.05)	Reject null hypothesis (H1)	ReUnion TSA System \geq Control (Benchmark) Sufficient evidence to reject the null hypothesis (H0: A - B < - θ) at the pre-determined significance level of 5%.

Table 3.1.1: Research Goal and Hypothesis (Primary Endpoint)

To test non-inferiority, the 24 months mean ASES Shoulder Score result of the ReUnion TSA System group will be compared to the mean estimate of the control group, 82.16 points.

To be able to identify an acceptable difference or zone of indifference ($-\theta$), the pooled standard deviation of the ASES Shoulder Score result at 24 months postoperative in the control group (Benchmark) was used as lower limit (pooled standard deviation of control is 16.76 points). The lower maximum acceptable difference ($-\theta$) is 65.40 points (mean of control - θ or 82.16 – 16.76 = 65.40 points).

Based on the underlying distribution of the data and the result of the normality assessment, either the parametric one-sample t-test or the non-parametric one-sample sign test will be used to compare the 24 months postoperative ASES Shoulder Score results of the ReUnion TSA System against the value of 65.40 points.

The analysis of the primary endpoint / objective will be conducted when all subjects have completed the 24 months postoperative including the ASES Shoulder Score.

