6.6. ANALYSIS OF CI ENDPOINTS

Evaluation Variable / Question	Level of Measurement	Analysis Plan					
Endpoints – Primary Endpoint							

Use variable Total ASES Shoulder Score 24 Months [points]: Based on the underlying distribution of the data and the result of the normality assessment, either the parametric one-sample t-test or the non-parametric one-sample sign test will be used to compare the 24 months postoperative ASES Shoulder Score results of the ReUnion TSA group against the lower maximum acceptable difference ($-\theta$) of 65.40 points.
 
The analysis of the primary endpoint will be part of the final report.
							

Table 6.6.1: Endpoints – Primary Endpoint Tables List

Evaluation Variable / Question	Level of Measurement	Recode and Analysis Plan	Inclusion		
Adverse Events – Time to (earliest) Device-Related Adverse Event / Incident			IR	FR	N/A
Creation of variable Difference between Date of Surgery [dd.mm.yyyy] and Date of First Device Related Adverse Event [dd.mm.yyyy] in days / (Variable(s): VISITDT; AEONSTDT)	Quantitative, ratio	Case summary with number and percentage of valid cases/values, missing cases/values (if any) and total cases/values. Mean, median, interquartile range, maximum, minimum, standard deviation, 95% confidence interval for mean, Shapiro-Wilk Test.		X	
Creation of variable Difference between Date of Surgery [dd.mm.yyyy] and Date of “most recent” Visit [dd.mm.yyyy] in days / (Variable(s): VISITDT)	Quantitative, ratio	N/A (Analyzed above), used for survivorship		X	

Create new variable “Grouping variable – First Device Related Adverse Event” (Variable(s): AEONSTDT)	Qualitative, nominal	- censored = survivors - events = first (earliest) Device Related Adverse Event		X	
Create new variable “Combined Time – First Device Related Adverse Event” (Variable(s): AEONSTDT)	Quantitative, ratio	- Use time between surgery and “most recent” visit for surviving subjects - Use time between surgery and first device related adverse event for subjects with device related adverse event		X	

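### A pass against 65.40 is reported as at or above the control mean of 82.16, which the test cannot show; the limit, null and sidedness are also stated inconsistently

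*Protocol*

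**What the plan says.** The only test named for the primary endpoint is a one-sample t-test or sign test of the 24-month ASES score against 65.40 (protocol 11.3.2; SAP 3.1.1 and 6.6). The control is the benchmark mean of 82.16.

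**Conclusions.** The protocol's decision table gives, for p ≤ 0.05, "ReUnion TSA System \geq Control (Benchmark) Sufficient evidence to reject the null hypothesis". For p > 0.05 both documents give the mirror statement, in the SAP "ReUnion TSA System < Control (Benchmark) Insufficient evidence to reject the null hypothesis". The text before the table explains non-inferiority as "meaning the clinical investigation result should be equal or better than the control" and ties the ≥ sign to that meaning. The same cells restate H0 with −θ, and the hypothesis table describes H1 as non-inferiority.

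**Limit.** Protocol 11.3.2 says that −θ "is 51.87 points (mean of control - θ or 82.16 - 16.76 = 65.40 points". SAP 3.1.1 gives 65.40 only. SAP 6.6 compares the "ReUnion TSA group against the lower maximum acceptable difference" and gives that difference as 65.40.

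**Null.** Protocol section 11 says that "the proposed study will test the null hypothesis that the population mean is 82.16 points", then tests against 65.40. Protocol Table 2 and SAP Table 3.2 repeat this.

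**Sidedness.** In protocol 11.3.2, "Hypothesis tests will be one-sided with a significance level" of 5%. SAP 3.1.1 agrees. The sample-size tables in both documents specify two tails.

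**Reporting.** Protocol 11.3.1 requires, for quantitative variables, "As variation parameter the standard deviation, 95% confidence interval of the mean".

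**The concern.** The hypotheses are set on a margin, but the conclusion column drops it. Rejecting a null at 65.40 supports a score above 65.40, that is, less than 16.76 points below the benchmark. It does not support a score at or above 82.16. In the other row, p > 0.05 is a failure to reject and is no evidence that the device is below control.

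Followed as written, the primary conclusion can therefore be contradicted by the confidence interval in the same report. The protocol says the study serves post-market requirements for safety and performance under the EU MDR, so this is the claim readers will rely on.

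The conflicting limit, null and sidedness are a lesser matter. They leave the decision rule without one clean statement, although a reader can work out which limit operates.

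**Working it through.** **Inputs.** Benchmark mean 82.16, SD 16.76 and limit 65.40 (protocol 11.3.2 and Table 2; SAP 3.1.1 and 3.2). One-sided α = 5% (protocol 11.3.2). Enrolment 100 and overall drop-out 56% (Table 2). No 24-month drop-out is given, so the evaluable n is an assumption: from 100 × (1 − 0.56) = 44, if all drop-out occurs by 24 months, to 100, if none does. The observed SD is taken as 16.76.

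**1. The plan's own figures.** 82.16 − 16.76 = 65.40, as stated. For power at n = 10, the standardised effect is (82.16 − 65.40)/16.76 = 1.0. Noncentral-t power is 80.31% two-sided at 5%, which reproduces the stated 80.3%. One-sided at 5% it is 89.75%. One-sided at 2.5% it is 80.31%.

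**2. The null as worded.** If the null were a mean of 82.16 and the true mean also 82.16, the rejection probability would be α, or 5%. So 80.3% belongs to a null of 65.40.

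**3. −θ as labelled.** On the A − B scale, 65.40 would put the pass line at 82.16 − 65.40 = 16.76, and 51.87 would put it at 82.16 − 51.87 = 30.29. Neither is the limit tested. The difference that gives 65.40 is 16.76.

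**4. Lowest observed mean that passes the t-test.** 65.40 + t(0.95, n−1) × 16.76/√n. The two-sided 95% half-width is t(0.975, n−1) × 16.76/√n. The highest mean whose interval still excludes 82.16 is 82.16 minus the half-width, taking 82.16 as fixed as the plan does.

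| | n = 44 | n = 100 |
|---|---|---|
| Lowest passing mean | 69.65 | 68.18 |
| Shortfall from 82.16 | 12.51 | 13.98 |
| 95% half-width | 5.10 | 3.33 |
| 95% CI at lowest pass | 64.55 to 74.74 | 64.86 to 71.51 |
| Highest mean with CI below 82.16 | 77.06 | 78.83 |

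Observed means from 69.65 to 77.06 (n = 44), or from 68.18 to 78.83 (n = 100), are labelled ≥ Control while their own interval excludes 82.16.

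**5. Sign test.** At exact one-sided 5%, 28 of 44 scores above 65.40 (p = 0.048) or 59 of 100 (p = 0.044) earn the same label.

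**6. How often, for illustration.** With a true mean of 72, about 10 points below the benchmark, the t-test passes with probability 82% (n = 44) or 99% (n = 100).

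**The case against.** The best defence is that ≥ is shorthand for non-inferiority. Table 2 and SAP Table 3.2 use it that way, the hypothesis table gives H1 with −θ, and each conclusion cell restates H0 with −θ. The column is headed as possible conclusions, SAP 6.6 specifies only the test, and the SAP section 7 templates do not require the phrase in a report. The mean and its 95% interval are reported anyway.

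This does not rescue the wording. The text before the table explicitly gives ≥ the meaning of equal or more than the control, and the p > 0.05 row is wrong on any reading.

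Other points do stand:

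- The 12.5 to 14.0 point shortfall follows from the one-SD margin, whose justification is a separate question. What is at issue here is the label put on such results.
- If the true mean is 82.16, as the plan assumes, an observed mean falls in the contradictory range only about 2% of the time. If it is 75, the figure is about 78% at n = 44.
- The benchmark is itself uncertain (95% interval 76.24 to 88.08 in Table 2). Against 76.24 the range shrinks to 69.65 to 71.14 (n = 44) or 68.18 to 72.91 (n = 100), but it does not vanish.
- Two-sided sizing with one-sided analysis is conservative, so power is not short.
- Moving the analysis to one-sided 2.5% would be a change of rule, not only of wording.

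**Conclusion.** The concern holds. Both conclusion cells are wrong as written and should be corrected before the 24-month analysis. A pass supports a mean less than 16.76 points below the benchmark (or, under the sign test, a median above 65.40). It does not support equality with or superiority to 82.16.

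The size of the problem rests on an SD of 16.76, 82.16 taken as fixed, and 44 to 100 evaluable subjects. On those terms the contradictory range is 7.41 points wide at n = 44 (77.06 − 69.65) and 10.65 points wide at n = 100 (78.83 − 68.18).

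The inconsistencies in limit, null and sidedness are drafting faults. Read with 65.40 and the stated one-sided 5% test, they do not change pass or fail. The 80.3% power figure and the subtraction giving 65.40 are both arithmetically correct.

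**What to change.** In protocol section 11, 11.3.2 and Table 2, and in SAP 3.1.1, 3.2 and 6.6:

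- State once: θ = 16.76 points; H0: mean ≤ 65.40; H1: mean > 65.40 (median in place of mean if the sign test is used).
- Delete 51.87 and the null of 82.16. Label 65.40 as the limit, not as −θ.
- Word a pass as: not worse than the benchmark mean by 16.76 points or more. Under the sign test, word it as: median above 65.40. Word a fail as: non-inferiority not shown.
- Remove equal or better as the meaning of a pass. Correct the decision cell that tags the rejected null hypothesis as H1.
- Report the observed mean minus 82.16 with a 95% interval, as description.
- Use one sidedness in sizing and analysis, and state it in protocol section 11 and SAP Table 4.7. Either keep one-sided 5% and restate power at n = 10 as 89.8%, or adopt one-sided 2.5%, which matches the stated 80.3%.

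**Cost.** Wording in two documents and one descriptive interval, with no change to enrolment. The headline claim becomes more modest. Keeping one-sided 5% leaves the pass line where it is. Choosing one-sided 2.5% raises the lowest passing mean to 70.50 (n = 44) or 68.73 (n = 100); power at a true mean of 82.16 stays above 99.9% at n = 44.

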This investigation is a prospective, multicenter clinical investigation. It is anticipated that a total of one hundred (100) subjects will be enrolled at approximately 4-7 sites. Neither subjects nor investigators are blinded to treatment and the clinical investigation does not include a contemporaneous control. The clinical investigation has been designed to follow the surgeon's standard of care for joint arthroplasty subjects, which entails clinical evaluation on a regular ongoing basis, or as needed should the subject become symptomatic in the treated joint. The enrollment period is expected to occur over 14 months.

8. Objective

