8.1. PRIMARY ENDPOINT

The primary endpoint of the clinical investigation is to demonstrate non-inferiority of the device to the selected literature controls, as measured by the ASES Shoulder Score at 24 Months post-operative.

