	
  
 	Cases	
 
 	Valid	Missing	
 
 	N	Percent	N	
   
 		
 
 		
 
 		
  
						Cases					Valid		Missing			N	Percent	N												
		Cases																													
		Valid		Missing																											
		N	Percent	N																											
				Total																											
		N	Percent	N																											
Mean ASES ReUnion_TSA_CER		10	100,0%	0	0,0%																										
Std.Dev. ASES ReUnion_TSA_CER		7	70,0%	3	30,0%																										
					10																										
					100,0%																										

 | | | |

Descriptives						
			Statistic			
Std.Dev. ASES ReUnion_TSA_CER			16,7571			
Mean 95% Confidence Interval for Mean			Lower Bound 12,6353 Upper Bound 20,8790			
Median Std. Deviation Minimum Maximum Interquartile Range			16,7000 4,45678 10,10 22,40 7,90			
Mean ASES ReUnion_TSA_CER			82,1600			
95% Confidence Interval for Mean			Lower Bound 76,2372 Upper Bound 88,0828			
Median Std. Deviation Minimum Maximum Interquartile Range			81,5000 8,27945 64,00 94,40 9,40			
						
Red line: Pooled mean ASES Blue lines: 95% CI of pooled mean ASES Black line: Pooled median pooled ASES Box: Interquartile Range Green Line: Pooled mean ASES minus pooled std. dev. ASES (16.76) $82.16 - 16.76 = \mathbf{65.40 \text{ points}}$						
Acceptance Criteria for Sample Size Calculation						
Significance Level (α)	0.05 (5%)					
Power (1-β)	0.80 (80%)					
Confidence Interval (CI)	0.95 (95%)					
Tails	2					
Path	Non-inferiority – ReUnion TSA (A) \geq Benchmark (B, explorative meta-analysis in this document)					
Hypotheses Pair	Null (H_0)		A – B $< -\theta$			
	Alternative (H_1)		A – B $\geq -\theta$			
Benchmark Timepoint	24 months post-operative					
Benchmark n (sources)	10					
Benchmark Mean	82.16 (pooled mean ASES [points])					
Benchmark Std. Dev.	16.76 (pooled std. dev. ASES [points])					
Benchmark Value	Pooled mean ASES minus pooled std. dev. ASES (16.76)					
Non-Inferiority Margin (-θ)	$82.16 - 16.76 = \mathbf{65.40 \text{ points}}$					
Software Used	IBM SPSS Sample Power V3.0					
IBM SPSS Sample Power Output						

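### The non-inferiority margin is one between-patient SD (16.76 points) with no matching rationale, so a significant test against 65.40 does not support the planned conclusion that the device is at least equal to the benchmark

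*Protocol*

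**What the plan says.** The primary question is non-inferiority to literature controls, "as measured by the ASES Shoulder Score at 24 Months post-operative" (Protocol 8.1). The study has one arm, and "the clinical investigation does not include a contemporaneous control" (Protocol section 7), so the test compares the sample with a constant.

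Protocol 11.3.2 explains why a margin is needed by pointing to sampling: "These estimates vary by a certain area, where it is expected that the true population parameter falls within". It then fixes the size of the margin: "the pooled standard deviation of the ASES Shoulder Score result at 24 months post-operative in the control group (Benchmark) was used as lower limit". SAP 3.1.1 says the same: "the pooled standard deviation of the ASES Shoulder Score result at 24 months postoperative in the control group (Benchmark) was used as lower limit". Protocol Table 2 (section 11.1) gives the benchmark value as "Pooled mean ASES minus pooled std. dev. ASES (16.76"), that is 82.16 − 16.76 = 65.40. The same table prints the 95% CI of the benchmark mean: "Lower Bound 76,2372 Upper Bound 88,0828".

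The test is a one-sample t-test or, depending on the normality assessment, a one-sample sign test against 65.40 (Protocol 11.3.2, SAP 3.1.1 and Table 6.6.1). On sidedness, Protocol 11.3.2 says "Hypothesis tests will be one-sided with a significance level α of 5"%, while the sample-size text in Table 2 is 2-tailed. The decision table in Protocol 11.3.2 and SAP Table 3.1.1 turns p ≤ 0.05 into the conclusion that the device is greater than or equal to the control. The surrounding text describes non-inferiority as a result equal to or better than the control.

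**The concern.** An SD measures how far individual patients differ from each other. It does not measure the uncertainty of a mean, which is the rationale the plan offers, and it does not say how much loss in the group mean would be acceptable, which is what a margin has to express. The margin therefore has no support in the reason written for it, and no other reason is given.

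Two consequences follow. First, noisier source studies would give a more lenient limit. Second, margin and SD are the same number, so the sample-size calculation contains no information about the ASES score.

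What is at stake is the wording of the only primary conclusion. A significant result excludes a mean of 65.40 or lower. The decision table reports it as a mean at or above 82.16.

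**Working it through.** **Inputs.** Benchmark mean 82.16, SD 16.76, limit 65.40, n = 10, power 80.3%, drop-out 56%, target 100 (all Protocol Table 2). Upper 95% limit for the SD 20.88 (Table 2). One-sided 5% (Protocol 11.3.2). The evaluable numbers are assumptions: 100 × (1 − 0.56) = 44 as the low case, and 100 as the high case. True deficits of 10 and 12 points are illustrations; the documents give no minimal important difference.

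**Formula.** One-sample t-test power from the noncentral t distribution with n − 1 degrees of freedom and noncentrality (true mean − limit) / (SD/√n).

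**1. The plan's own figure.** Noncentrality = (82.16 − 65.40)/(16.76/√10) = √10 = 3.162. At two-sided 5% and 9 degrees of freedom, power is 80.31%. The stated 80.3% reproduces.

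**2. Why that figure is not about ASES.** With margin = SD, noncentrality is SD/(SD/√n) = √n whatever the SD. Putting in 10.1 or 22.4 (the extremes of the reported SDs), with the margin moved to match, again gives 80.31%.

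**3. Margin against the stated rationale.** The ten source means have SD 8.279, so the standard error is 8.279/√10 = 2.618. The CI is 82.16 ± 2.262 × 2.618 = 76.24 to 88.08, as printed, with half-width 5.92. The margin is 16.76/5.92 = 2.8 times that half-width. The limit of 65.40 lies below nine of the ten source means (lowest 64, next 77.9).

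**4. Smallest observed mean that passes** (sample SD 16.76, one-sided 5%).
- n = 44: 65.40 + 1.681 × 16.76/√44 = 65.40 + 4.25 = 69.65, which is 12.5 points below 82.16.
- n = 100: 65.40 + 1.660 × 16.76/√100 = 65.40 + 2.78 = 68.18, which is 14.0 points below.

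**5. Chance that a device with true mean 72.16 passes** (10 points below). At n = 44 the noncentrality is 6.76/2.527 = 2.675; at n = 100 it is 6.76/1.676 = 4.033.

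| Rule | n = 44 | n = 100 |
|---|---|---|
| t-test, one-sided 5%, SD 16.76 | 84% | 99% |
| t-test, two-sided 5%, SD 16.76 | 74% | 98% |
| t-test, one-sided 5%, SD 20.88 | 68% | 94% |
| sign test, one-sided 5%, SD 16.76 | 67.5% | 93% |

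The sign-test row assumes normal scores: each subject exceeds 65.40 with probability Φ(6.76/16.76) = 0.657, and 28 of 44 or 59 of 100 must do so. At n = 10 the one-sided t-test would pass such a device only 32% of the time.

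**6. Larger and limiting deficits** (one-sided t-test, SD 16.76). At 12 points below, 58% pass at n = 44 and 88% at n = 100. At a true mean of exactly 65.40, 5% pass.

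**7. A tighter limit, as an example.** Against 76.24 with true mean 82.16 and SD 16.76, one-sided t-test power is 75% at n = 44 and 97% at n = 100. The sign test has 58% at n = 44. With SD 20.88 and n = 44 these fall to 58% (t-test) and 43% (sign test).

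**The case against.** The strongest defence is that the test does control error at the limit it names: a device at 65.40 passes only 5% of the time. This stands. The fault lies in how the limit was chosen and how a pass is worded.

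SAP Table 6.5.2 also requires the total ASES mean, SD and 95% CI at every visit in interim and final reports, so a careful reader could see the distance from 82.16. This stands too and limits the harm, but the formal conclusion would still contradict those figures.

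The pass rates depend on choices the plan leaves open. The sign test, the two-sided reading and a larger SD all lower the 84%. All three stand and are shown above; a 10-point deficit still passes about two times in three or more at 44 evaluable.

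Finally, any replacement such as half the SD (73.78) or the lower CI limit (76.24) would again rest on patient spread or on the spread of the source means, with no clinical justification in the documents. That stands, so this review does not prescribe a limit.

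A reader might infer that the test cannot tell a comparable device from a worse one, or that a pass is close to certain. The figures do not support this in general: at 44 evaluable a 12-point deficit passes 58% of the time. Near-certainty holds for devices close to the benchmark, or for a deficit of about 10 points at 100 evaluable, and 100 is a target, not achieved enrolment. Nor do the documents allow 10 points to be called clinically worse.

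**Conclusion.** The point holds as a mismatch between margin, rationale and conclusion. The margin is one between-patient SD, 2.8 times the half-width of the benchmark CI that the stated rationale points to, and it has no clinical justification in the visible text. A significant result shows only that the mean is above 65.40, yet it would be reported as at or above the benchmark even with an observed mean of about 69.6 (n = 44) or 68.2 (n = 100). The 10-case, 80.3% calculation is correct arithmetic but follows from setting margin equal to SD.

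The sizes assume SD 16.76 unless stated, 44 to 100 evaluable at 24 months, and one test on all subjects together. The 44 applies the plan's overall drop-out rate, whose cited source is a follow-up of at least 10 years, so the number at 24 months may be higher and the pass rates nearer the n = 100 column. The 10-point deficit is illustrative.

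**What to change.** 1. In Protocol 11.3.2 and SAP 3.1.1 and 6.6, replace the equal-or-better conclusion with: mean 24-month ASES not more than 16.76 points below the benchmark of 82.16. Refer to the median if the sign test is used.
2. Report the one-sided 95% lower confidence bound for the 24-month mean (or median) beside 82.16 and the benchmark CI of 76.24 to 88.08, so that the largest deficit not excluded is visible.
3. State in Protocol Table 2 and SAP Table 3.2 that n = 10 follows from setting θ equal to the SD.
4. Either justify 16.76 points, or prespecify a tighter, justified limit tested after 65.40 in fixed order on the same data. The limits are nested on one parameter and the second is tested only if the first is passed, so no alpha is spent. The choice of limit is the sponsor's; the powers for 76.24 in the working show what one such limit would cost.
5. While editing, reconcile two related items: Protocol 11.3.2 prints 51.87 where its own arithmetic and the SAP give 65.40, and sidedness differs between Table 2 and 11.3.2.

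The cost is wording in two documents, with no extra subjects or data. The downside is a less favourable claim, and any tighter second step may fail if few subjects are evaluable.
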